COVER PAGE

DCP Protocol #: UAZ2017-09-02 Local Protocol #: 1711022046

Clinical Study of Avmacol® for Detoxification of Tobacco Carcinogens in Heavy Smokers

Consortium Name: Name of Consortium Principal Investigator:	The University of Arizona Early Phase Cancer Prevention Consortium [name] [name] University of Arizona Cancer Center [name] [contact]; [contact] [contact]
Organization Name: Protocol Principal Investigator:	University of Arizona [name], MPH The University of Arizona, Arizona Cancer Center [name] [contact]; [contact] [contact]
Organization: Statistician:	University of Arizona [name] The University of Arizona Cancer Center [name] [contact]; [contact] [contact]
Medical Monitor:	[name] Medical Officer and Chief Lung & Upper Aerodigestive Cancer Research Group Division of Cancer Prevention, NCI, NIH [name] [name], MD 20850 [contact]; [contact] Email: [contact]
IND Sponsor:	NCI/Division of Cancer Prevention
IND#	
Agent(s)/Supplier:	Avmacol® /Nutramax
NCI Contract #	HHSN2612012000311
Protocol Version Date:	10.17.18
Protocol Revision or Amendment # DCP Protocol Template Version 8.5	Version 3, Amendment 6
08/31/2016	

SCHEMA

Clinical Study of Avmacol® for Detoxification of Tobacco Carcinogens in Heavy Smokers

Current smokers with ≥ 20 pack years self-reported smoking history and a current average use of ≥ 10 cigarettes/day

Visit 1: Screening

Informed consent, clinical evaluation (medical history, vital signs, brief physical exam), clinical labs, conmeds and supplement use, Karnofsky performance status, baseline tobacco/alcohol assessment, pregnancy test (if applicable)

Randomization

High-Low Arm or Low-High Arm

Visit 2: Baseline Specimen Collection for Intervention Period 1

Collection of buccal cells, nasal brushing and blood, AEs, conmeds, current tobacco use, pregnancy test (if applicable),

ensure overnight urine collection, dispense study agent

Intervention Period 1 (10-14 days) High-Low Arm: 8 tablets Avmacol® per day or Low-High Arm: 4 tablets of Avmacol® per day

Visit 3: Interim Visit (Intervention Period 1, (may occur on Day 4 to Day 8) Collection of buccal cells, AEs, conmeds, current tobacco use

,

Visit 4: End-of-Intervention Period 1Visit

Collection of buccal cells, nasal brushing and blood, AEs, conmeds, current tobacco use, ensure overnight urine collection, study agent return, compliance

1. OBJECTIVES

1.1 **Primary Objective**

To determine whether Avmacol® increases the urinary excretion of the mercapturic acid of the tobacco carcinogen, benzene, in healthy volunteers who are current heavy smokers.

1.2 Secondary Objectives

- To determine whether Avmacol® increases the urinary excretion of the mercapturic acids of other tobacco carcinogens, including acrolein and crotonaldehyde;
- To determine whether Avmacol® increases the urinary excretion of the mercapturic acids of tobacco carcinogens, normalized by bio-measurement of tobacco exposure;
- To determine whether Avmacol® upregulates the NRF2 target gene transcripts in the buccal cells of current smokers;
- To evaluate for a dose-response relationship between Avmacol® and the detoxification of tobacco carcinogens and the expression of NRF2 target gene transcripts.
- To determine the relationship between systemic study agent exposure and biomarker modulation.

1.3 Exploratory Objectives

- To determine whether the *GSTM1* and *GSTT1* genotypes are important genetic modulators of detoxification of tobacco carcinogens with Avmacol® treatment;
- To bank specimens for future research including evaluation of tobacco gene signatures in buccal and nasal epithelium and buccal cell nuclear morphometry.

2. BACKGROUND

2.1 Tobacco-related Head and Neck Cancer

Long-term success in the treatment of tobacco-related head and neck squamous cell carcinoma (HNSCC) is hindered by an alarming rate of second primary tumor (SPT) formation following curative treatment. Patients with human papillomavirus (HPV)-negative HNSCC develop a SPT of the upper aerodigestive tract at the rate of 3-6% per year, and are most likely to succumb to these secondary cancers (1-4). Although smoking cessation reduces the occurrence of SPTs, moderation of risk is not observed for 5 years, and is insufficient to return risk to baseline (3, 5). Moreover, although 70% of smokers attempt to quit annually, tobacco cessation is unsuccessful in the majority due to the power of nicotine addiction, and recidivism occurs in approximately 90% (6). Thus, most tobacco users are unable or unwilling to quit, and those who do succeed still face chronic exposure to the endogenous carcinogens of metabolism or the exogenous carcinogens of industrialization.

The concept of "condemned mucosa", or epithelial field cancerization from chronic exposure to environmental carcinogens, first raised the possibility of chemoprevention for HNSCC in 1953 (7); however, no nontoxic, effective chemopreventive agent has been identified. When epidemiologic studies found that reduced risk for both HNSCC and SPTs is associated with diets rich in fruits and vegetables (8-12), the first chemoprevention strategies focused on pharmacologic doses of derivative micronutrients. Preclinical models supported retinoids, synthetic vitamin A analogues, as modulators of oral environmental carcinogenesis (13, 14). Although high dose isotretinoin reversed oral premalignant lesions (OPLs) (15) and prevented SPTs in a landmark Phase III HNSCC chemoprevention study (16), substantial toxicity precluded chronic administration and SPT incidence reverted to baseline within 3 years. A subsequent trial of low dose isotretinoin was tolerable but ineffective (17). Molecular targeting of EGFR or COX-2 has shown preclinical chemopreventive efficacy against oral cancer (18-22), but clinical application has been hampered by poor efficacy and tolerability in humans (23-27). Thus, a tremendous unmet need remains for an effective and well-tolerated chemopreventive agent against tobacco-related HNSCC and SPTs.

2.2 Avmacol®

Epidemiologic studies report that reduced risk for both HNSCC and SPTs is associated with diets rich in the Brassica family of cruciferous vegetables (8-12). Broccoli extract potently induces cytoprotective enzymes (28), which mitigate the effects of environmental carcinogens including benzene, aldehydes and polycyclic aromatic hydrocarbons found in tobacco smoke by enhancing their detoxication (29, 30). More than 80% of inducer activity is driven by the phytochemical sulforaphane (SF), produced when its precursor glucoraphanin (GR) is hydrolyzed by myrosinase during food preparation or chewing (31). Mechanistically, SF disrupts the polyubiquitination of the NRF2 transcription factor mediated by its inhibitory protein, KEAP1. This frees NRF2 to translocate to the nucleus and bind to anti-oxidant response elements (AREs) in the promoter regions of target genes (32, 33). As GR is 20-50 times more concentrated in broccoli seeds relative to mature plants (31, 34), we are developing broccoli seed preparations (BSPs) as a chemopreventive agent against carcinogen-induced cancers, and have determined the safety and pharmacokinetics (PK) of various BSPs in humans (33, 35-39).

Two types of highly standardized, lyophilized boiling water extracts of 3-day-old broccoli sprouts have been developed by our collaborators ([name], [name]) at the Johns Hopkins Cullman Chemoprotection Institute under GMP conditions, and used extensively under clinical protocols – including our own pilot study evaluating the oral bioactivity of broccoli sprout extracts (BSE) in the oral mucosa of healthy volunteers (NCT02023931) (39). However, there are three main problems in achieving consistent delivery and bioavailability of active SF by means of lyophilized BSE: (1) SF is only moderately storage- and heat-stable over time, especially in aqueous solution. (2) SF-rich BSE powders are extremely hygroscopic and the preparation of capsules containing accurate doses by weight is challenging and very expensive. (3) Administration of GR as an oral precursor of SF results in highly variable conversions of GR to SF metabolites (dithiocarbamates) among individuals, ranging from 1 - 40% (35, 38, 40-42). Moreover, the curated GMP manufacturing process for BSEs is laborious and expensive, and consequently BSE is no longer available for clinical investigation.

Avmacol® is a commercially available dietary supplement that contains GR plus the fully active enzyme myrosinase, thus yielding a higher and more consistent dose of SF upon ingestion. Avmacol® tablets contain only GR-rich broccoli seed extract, freeze-dried broccoli sprouts for the myrosinase source, and the inert excipients required to form a tablet. Avmacol® is manufactured by Nutramax Laboratories, Inc., has been sold as a nutritional supplement in the United States since 2013, and is manufactured under GMP standards. The coated tablets contain 12.5 mg of GR, and have a minimum shelf life of 30 months at ambient temperature. We have completed a healthy volunteer study confirming the bioavailability of SF when delivered as Avmacol® (NCT02800265), and this dietary supplement is now under investigation as a chemoprevention agent in multiple disease contexts, including the detoxication of air pollutants in Qidong, China ([name]).

DCP Protocol Template Version 8.5 08/31/2016

2.3 Rationale

Proof-of-concept clinical trials in healthy volunteers have shown that BSPs rich in GR and/or SF are well-tolerated and promote rapid, sustained detoxication of the airborne pollutants acrolein and benzene (33, 35-38). In preclinical studies, SF has exhibited chemopreventive activity against carcinogen-induced stomach, skin and breast cancers (43-47). Studies in $Nrf2^{-/-}$ mice have shown that the chemopreventive effect of sulforaphane against benzo[a]pyrene-induced gastric cancer and 7,12-dimethylbenz(*a*)anthracene (DMBA)-induced skin cancer depends on the NRF2 signaling pathway (43, 44, 47). The relevance of NRF2 to oral cancer chemoprevention is highlighted by the enhanced susceptibility of $Nrf2^{-/-}$ mice to oral cancer induced by the carcinogen 4-nitroquinoline-1-oxide (4NQO), and the reduced susceptibility of *Keap1*^{-/-} mice (48). We have shown that SF induces NRF2 and NRF2 target gene expression in normal oral keratinocytes and in HNSCC cell lines *in vitro*. In a preclinical chemoprevention study, we have determined that SF reduces both the incidence and total burden of oral tumors in 4NQO-treated mice. Finally, we have observed mucosal bioactivity of two well-tolerated BSPs, sulforaphane-rich BSE and Avmacol® ((39); unpublished data NCT02800265), which both upregulated transcripts for the NRF2 target gene *NQO1* in the buccal mucosa of healthy volunteers.

2-Phenethyl isothiocyanate (PEITC), another glucosinolate present in certain cruciferous vegetables including watercress and broccoli sprouts, has been demonstrated to have multiple chemoprotective effects on xenobiotic metabolizing enzymes and molecular pathways related to cancer (1, 2). In a randomized, crossover study, PEITC promoted detoxication of benzene and acrolein in a healthy smoking population (49). A much stronger effect was observed among subjects with the null genotype of both *GSTM1* and *GSTT1*. Due to established mechanisms of action, SF-rich BSPs are likely to be more effective inducers of NRF2 target genes and consequent detoxication of tobacco carcinogens in this population. Moreover, in a 300-patient study in Qidong, China, the upregulation of the urinary excretion of the mercapturic acid of benzene by broccoli sprout extracts was independent of *GSTM1* and *GSTT1* genotypes, suggesting broader applicability of this green chemoprevention strategy across a general population (38).

In the proposed trial, we aim to evaluate the pharmacodynamic activity of Avmacol® in healthy current heavy smokers. The primary objective is to determine whether Avmacol® increases the urinary excretion of the mercapturic acid of the tobacco carcinogen, benzene in healthy volunteers who currently smoke. Secondary objectives include: 1) to determine whether Avmacol® increases the urinary excretion of the mercapturic acids the tobacco carcinogens, acrolein, and crotonaldehyde; 2) To evaluate for a dose-response relationship between Avmacol® and the detoxification of tobacco carcinogens and the expression of NRF2 target gene transcripts; 3) to determine whether NRF2 target genes are upregulated in the mucosa of current smokers. Exploratory objectives include: 1) to determine whether the *GSTM1* and *GSTT1* genotypes are important genetic modulators of detoxication of tobacco carcinogens during Avmacol® treatment; 2) to bank biospecimens for future study, including the evaluation of tobacco gene signatures in buccal and nasal epithelium, as well as buccal cell nuclear morphometry.

Increasing evidence suggests that tobacco and alcohol use are risk factors in the development of intraepithelial neoplasia and cancer. In addition, tobacco and alcohol use may adversely affect agent intervention, for example by altering the safety profile or metabolism of a drug. Standardized assessments of tobacco and alcohol use during clinical trials will aid in understanding the potential relationship between the use of these products and clinical endpoints or cancer prevention biomarkers. Therefore, NCI, DCP is including assessment of tobacco and alcohol use at baseline and at the End of Intervention visit, to determine the potential impact of tobacco and alcohol use on 1) treatment toxicity and symptom burden, and 2) the efficacy of treatment intervention.

3. SUMMARY OF STUDY PLAN

This is an open-label, randomized, cross-over study, evaluating whether two different doses of Avmacol® (4 tablets per day for 10-14 days; 8 tablets per day for 10-14 days) increase the detoxification of tobacco carcinogens in otherwise healthy, current heavy smokers. Participants will serve as their own controls. We chose the open-label design because the study endpoints are not likely to be affected by the knowledge of the dosage assignment. We believe that the proposed randomized cross-over design would minimize the potential bias from the open-label design. We plan to accrue 61

eligible participants to initiate agent intervention. With an anticipated attrition rate of 33% or less (with respect to completing the intervention and having complete endpoint data), we expect to have at least 41 participants with evaluable endpoint data. Projected accrual is 2 participants per month.

Participants will undergo a screening evaluation (Visit 1) in which the informed consent form will be signed. Participants will be assessed for study eligibility. Detailed inclusion and exclusion criteria are listed in sections 4.1 and 4.2. All participants will undergo evaluation to obtain height, weight, blood pressure, pulse, temperature measurements, a brief physical exam consisting of an examination of the heart, lungs and abdomen, and Karnofsky performance status assessment. They will also be evaluated for concurrent medication and supplement use, baseline tobacco/alcohol assessment, medical history, and laboratory analysis with complete blood count with differential (CBC-diff), comprehensive metabolic panel (CMP). Women of childbearing capacity will have a urine pregnancy test. Study participants will be provided with a daily diary for recording any adverse events (AEs) and medication usage and a urine collection kit (an overnight urine collection container, a collection hat, and instructions for collecting overnight urine) to be used the night prior to Visit 2.

Once determined eligible, participants will be randomized (1:1) to one of the following arms: High-Low Arm (8 tablets Avmacol® per day during Intervention Period 1 and 4 tablets Avmacol® per day during Intervention Period 2) and Low-High Arm (4 tablets Avmacol® per day during Intervention period 1 and 8 tablets Avmacol® per day during Intervention Period 2).

Participants will return to the clinic for Baseline Specimen Collection for Intervention Period 1 (Visit 2). Participants will be contacted prior to the visit to remind them to collect overnight urine the night prior to Visit 2. Participants will bring the overnight urine to the clinic and undergo baseline specimen collection for the collection of buccal cells (for NRF target gene transcripts), nasal brushing (banked for gene expression analysis) and blood (for genotyping and banking). Participants will be assessed for baseline symptoms, concomitant medications, and be queried on current tobacco use. Urine pregnancy test will be repeated, if applicable. Those who miss the overnight urine collection prior to Visit 2 will be asked to collect overnight urine the night of the visit and return the urine to the clinic the following day. Participants will be provided with Avmacol® pills for Intervention Period 1 after confirmation of overnight urine collection. Participants will be provided with an Intake Calendar for recording agent intake.

During Intervention Period 1 (10-14 days), participants in the High-Low Arm will take 8 tablets of Avmacol® each day and participants in the Low-High Arm will take 4 tablets of Avmacol each day. Participants will be instructed to take the Avmacol® pills with the evening meal. Day 1 of the Intervention Period 1 begins the day the first dose is taken. During Intervention Period 1, participants will return to the clinic on Day 4, 5, 6, 7, or 8 for an Interim Visit (Visit 3). Participants will undergo the collection of buccal cells and be assessed for AEs, concomitant medications and be queried on current tobacco use. Participants will be provided with a new urine collection kit to be used the night prior to Visit 4.

Participants will return to the clinic at the end of Intervention Period 1 (Visit 4). Participants will be contacted prior to this visit to remind them to collect overnight urine the night prior to Visit 4. Participants will bring the overnight urine to clinic, return unused pills, undergo specimen collection for the collection of buccal cells, nasal brushing and blood. Participants will also be assessed for AEs, concomitant medications, compliance, and be queried on current tobacco use. Those who miss the overnight urine collection prior to Visit 4 will be provided with additional Avmacol® pills and be asked to take the pills the evening of Visit 4 and collect overnight urine the night of the visit and return the urine to the clinic the following day. Participants will be provided with a new urine collection kit to be used the night prior to Visit 5.

Participants will undergo a Washout Period (10-14 days) after completing Intervention Period 1. After the Washout Period, participants will return to the clinic (Visit 5) to undergo baseline specimen collection for Intervention Period 2. Participants will be contacted prior to the visit to remind them to collect overnight urine the night prior to Visit 5. Participants will bring the overnight urine to the clinic and undergo baseline specimen collection for the collection of buccal cells, nasal brushing and blood. Participants will also be assessed for AEs, concomitant medications, and be queried on current tobacco use. Urine pregnancy test will be repeated, if applicable. Those who miss the overnight urine

collection prior to Visit 5 will be asked to collect overnight urine the night of the visit and return the urine to the clinic the following day. Participants will receive Avmacol® pills for Intervention Period 2 after the overnight urine collection is confirmed.

During Intervention Period 2 (10-14 days), participants in the High-Low Arm will take 4 tablets of Avmacol® each day and participants in the Low-High Arm will take 8 tablets of Avmacol® each day. Participants will be instructed to take the Avmacol® pills with the evening meal. Participants will be provided with an Intake Calendar for recording agent intake. Day 1 of the Intervention Period 2 begins the day the first dose is taken. During Intervention Period 2, participants will return to the clinic on Day 4, 5, 6, 7, or 8 for an Interim Visit (Visit 6). Participants will undergo the collection of buccal cells and be assessed for AEs, concomitant medications and be queried on current tobacco use. Participants will be provided with a new urine collection kit to be used the night before Visit 7.

Participants will return to the clinic at the end of Intervention Period 2 (Visit 7). Participants will be contacted prior to the visit to remind them to collect overnight urine the night prior to Visit 7. Participants will bring the overnight urine to clinic, return unused pills, undergo specimen collection for the collection of buccal cells, nasal brushing and blood. Participants will also be assessed for AEs, concomitant medications, compliance, and follow-up tobacco/alcohol assessment. Additional blood samples will be collected for safety labs (CBC-diff and CMP). Those who miss the overnight urine collection prior to Visit 7 will be provided with additional Avmacol® pills and be asked to take the pills the evening of Visit 7 and collect overnight urine the night of the visit and return the urine to the clinic the following day.

After completion of Intervention Period 2, participants will be provided with information on how to contact the Arizona Smokers' Helpline (toll free telephone number and URL to access the ASHLine website), which provides comprehensive services for tobacco cessation.

Participants will be contacted by telephone (or email) 10-14 days after completing Intervention Period 2 for a final AE assessment and be reminded to return the AE Diary to the study office.

4. PARTICIPANT SELECTION

4.1 Inclusion Criteria

- 4.1.1 Male or female current tobacco smokers with ≥ 20 pack years of self-reported smoking exposure and a current average use of ≥ 10 cigarettes/day.
- 4.1.2 Age ≥ 18 years.
- 4.1.3 Karnofsky performance scale \geq 70% (see Appendix A).
- 4.1.4 Participants must have normal organ and marrow function as defined below:

Leukocytes	\geq 3,000/microliter
Absolute neutrophil count	\geq 1,500/microliter
Platelets	\geq 100,000/microliter
Total bilirubin	$\leq 2 \times$ institutional upper limit of normal (ULN)
AST (SGOT)/ALT (SGPT)	$\leq 1.5 \times \text{ULN}$
Creatinine	\leq ULN

4.1.5 Fertile subjects must use adequate contraception (abstinence, barrier methods, or birth control pills) prior to study entry and for the duration of study participation. The effects of Avmacol® on the developing human fetus are unknown. For this reason women of child-bearing potential and men must agree to use adequate contraception (hormonal or barrier method of birth control; abstinence) prior to study entry and for the duration of study

participation. Should a woman become pregnant or suspect she is pregnant while participating in this study, she should inform her study physician immediately.

4.1.6 Ability to understand and the willingness to sign a written informed consent document.

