13.4 Primary Objective, Endpoint(s), Analysis Plan

The primary objective of this study is to determine whether Avmacol® increases the urinary excretion of the mercapturic acid of the tobacco carcinogen, benzene, in healthy current smokers. The primary endpoint is the change (from baseline to end-of-intervention for each Intervention Period) in the mercapturic acid of benzene after Avmacol® intervention. The changes following 4 tablets of Avmacol® per day and after 8 tablets of Avmacol® per day will be determined separately. Two-sided paired t tests will be performed to evaluate whether the changes are significantly. Bonferroni correction will be used to correct for multiple comparisons (two dose levels). With a sample size of 41 and an overall significance level of 5% (based on Bonferroni correction, i.e. a 2.5% significance level for each test), there will be at least 80% power to detect an effect size of 0.50 standard deviations. This is in line with an effect size of 0.45 standard deviations for a similar study (49).

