13.8 Evaluation of Response

All subjects with endpoint data will be assessed for response to intervention, based on the endpoints described above in Sections 13.4 and 13.5.

Sub-analyses may be performed on the subsets of participants, excluding those for whom major protocol deviations have been identified (e.g., early discontinuation of intervention, major protocol violations, etc.). However, sub-analyses may not serve as the basis for drawing conclusions concerning efficacy, and the reasons for excluding participants from the analysis should be clearly reported.

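### Eligibility does not screen out smokers about to quit or cut down, although the uncontrolled before-after primary test has no power in reserve: a cheap improvement

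*Combined protocol and SAP*

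**What the plan says.** **Eligibility.** Section 4.1 asks for at least 20 "pack years of self-reported smoking exposure and a current average use of" at least 10 cigarettes a day. Neither 4.1 nor 4.2 mentions intention to quit or reduce, cessation aids, or stable smoking.

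**Background rate.** Section 2.1 states that "although 70% of smokers attempt to quit annually". The same sentence adds that cessation fails in the majority and that about 90% relapse.

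**Primary analysis.** Sections 8.1 and 13.4 define the endpoint as the change from baseline to end of intervention in the benzene mercapturic acid, normalised by urinary creatinine. Each dose gets its own paired t test, at "a 2.5% significance level for each test", two-sided. For 41 evaluable participants, Section 13.4 says "there will be at least 80% power to detect an effect size of 0.50 standard deviations".

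**Who is analysed.** Section 13.8: "All subjects with endpoint data will be assessed for response to intervention". Sub-analyses that leave out major deviations may not support efficacy conclusions. Quitting is not among the off-agent or off-study reasons in 8.3 and 8.4.

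**What the plan does have on smoking.** A footnote to the Schedule of Events (7.1) has participants asked at each visit whether they have smoked at least 10 cigarettes a day since the previous one. Section 8.2 makes the mercapturic acids normalised by total urinary nicotine and metabolites a secondary endpoint. Section 13.5 allows regression for potential confounders where needed, and a transformation or signed rank test if normality fails.

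**The concern.** The marker tracks smoke intake, so the before-after change reads as an agent effect only if smoking is about the same before both urines. There is no placebo or untreated period. Randomisation sets only the order of the doses, and each dose's change is tested on its own, so no concurrent control absorbs a change in smoking.

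A participant who cuts down between the two urines shows a fall in the metabolite whatever the agent does. One or two such participants among 41 lower the mean change and widen its SD, so a real effect may be missed. The opposite error is also possible: an attempt during washout lowers the Visit 5 baseline, and relapse in Period 2 then looks like benefit.

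**Working it through.** **1. The plan's own power.** Inputs from 13.4: n=41, effect 0.50 SD of the paired change, two-sided alpha 0.025. Noncentral t with df=40 and noncentrality 0.50×√41 = 3.20 gives 80.5%. The stated figure reproduces, and 41 is the smallest n that reaches 80%. At 0.45 SD, the effect that 13.4 attributes to a similar study, the same calculation gives 71%.

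**2. Attempts per period.** Assume that 70% a year is a constant rate and applies to these participants. The share with a first attempt in d days is 1 − 0.30^(d/365).
- 10 days: 3.2%, or 1.3 of 41
- 12 days: 3.9%, or 1.6 of 41
- 14 days: 4.5%, or 1.8 of 41
- 21 days (the longest period that 7.1 permits): 6.7%, or 2.7 of 41

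**3. Share still reduced at the end urine.** The documents give no time course for relapse. If all attempts persist, the share is about 4%. If the 90% relapse figure in 2.1 has already taken full effect, it is 0.1 × 3.9% = 0.39%. The range below covers both.

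**4. Effect on power.** Assume a log-scale SD of change of 0.5; the documents give none. A fraction q has its change shifted down by k SD: k = ln 2/0.5 = 1.39 if smoking is halved, and k = ln 10/0.5 = 4.61 if the metabolite falls by 90%. The mean becomes 0.50 − qk and the SD √(1 + q(1−q)k²). Example, q=4% and smoking halved: mean 0.50 − 0.04×1.39 = 0.445, SD √(1 + 0.04×0.96×1.39²) = 1.036, effect size 0.43, power 66%. The 90% cases are strongly skewed, so power there comes from simulation of the same model (values move by about a point between runs).

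| Still reduced at end urine | t test, smoking halved | t test, metabolite down 90% | signed rank, metabolite down 90% |
|---|---|---|---|
| 0.4% | 79% | 74% | 76% |
| 1% | 77% | 64% | 72% |
| 2% | 74% | 50% | 65% |
| 4% | 66% | 28% | 50% |

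With SD 0.8 and 4% reduced, t-test power is about 73% (halved) or 46% (down 90%).

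**5. Check without a log-scale SD.** Let every attempt persist and lower the change by k SD.
- 3.2%: 77% (k=0.5), 73% (k=1), 62% (k=2)
- 4.5%: 76%, 70%, 54%
- 6.7%: 74%, 64%, about 42%

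**The case against.** The strongest reply is that the plan already measures smoking and can see the problem. The nicotine-normalised endpoint is prespecified, covers the tobacco carcinogens including benzene, and uses the same overnight urines. Smoking is asked about at every visit, and the follow-up questionnaire asks about it during treatment. Concomitant medications are recorded, which would show cessation aids, and are a possible off-agent reason. Regression is available, and helpline details are given only after Period 2. So it would be wrong to infer that the plan ignores changes in smoking.

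These measures allow a check but do not protect the primary test. The visit query is yes/no at 10 cigarettes a day, so a cut from 30 to 12 goes unseen, and a no has no stated consequence in the analysis. Regression is discretionary and does not name smoking. The nicotine-normalised result is secondary, and nicotine from a cessation aid would enter its denominator.

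Three further objections hold and limit the size of the point:
- The 70% counts attempts in a year among smokers in general, not reductions that last to the end urine. A reader might take 4% as the expected share still reduced; Section 2.1 does not support that.
- A reader might take 28% as the power of the planned analysis. In that case, normality would be visibly violated, and the 13.5 fallback to signed rank gives about 50%.
- Screening on stated intention cannot prevent unplanned attempts, so it does not guarantee a return to 80.5%.

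**Conclusion.** The omission is real and worth correcting, as a cheap improvement and not as a flaw that undermines the trial. About 1-2 of 41 participants would make an attempt in a 10-14 day period, and fewer would still be reduced at the end urine. The loss of power runs from about one point (0.4% still reduced, smoking halved) to a serious loss only if nearly every attempt persists and the metabolite falls by 90%.

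Two stronger readings do not hold. One is that quit attempts always appear as loss of effect. Dilution and extra variance are the main result, but the washout-then-relapse route inflates the change. The other applies the whole-participation figures, 1 − 0.30^(42/365) = 13% over 42 days or 21% over 70, to the primary test. Each dose's change spans a single period of at most 21 days.

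The sizes rest on assumptions that the documents do not settle: a constant attempt rate, the 70% applying to these smokers, the SD of the log change, the depth of the fall, and how many attempts last to the end urine. What does not depend on them is that eligibility is silent on intention, the primary test is uncontrolled, and n=41 leaves no reserve.

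**What to change.** Add to Section 4.2 an exclusion for anyone who intends to stop or reduce smoking, or who has started or plans to start a smoking-cessation aid, during the participation period. Ask it in the telephone pre-screen described in 7.2, which already covers smoking history, and again at Visit 1. State that a participant who later decides to quit remains free to do so.

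Because this cannot stop unplanned attempts, also name in 13.4 the nicotine-normalised benzene result from 8.2 as the key sensitivity analysis for the primary test. The measurement is already planned. Keeping users of cessation aids out also protects its denominator.

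Cost: one eligibility line, one screening question and one sentence in the analysis plan, by amendment. The downside is slightly slower accrual and a population limited to smokers who are not about to quit.
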